## FLE-002 (INSTANT) – Final Analysis

## Statistical Analysis Plan

- LVEF is  $\geq 45\%$
- LV hypertrophy is “Absent” or “Mild”
- Aortic Valve Disease (stenosis or regurgitation) is “Absent” or “Mild”
- Mitral Valve Disease (stenosis or regurgitation) is “Absent” or “Mild”

Subject is considered non eligible if any condition below is applicable:

- LVEF is  $< 45\%$
- LV hypertrophy is “Moderate” or “Severe”.
- Aortic Valve Disease (stenosis or regurgitation) is “Moderate” or “Severe”.
- Mitral Valve Disease (stenosis or regurgitation) is “Moderate” or “Severe”.

Subject is considered non assessable if all conditions below are applicable:

- None of the four conditions indicated in the category “non-eligible”, as indicated above, apply
- For at least one of the four characteristics used in the category “non-eligible” a missing value occurs.

### **9.2.4.3 *Subject considered ineligible as a result of HHE assessment***

The independent review will not be used for the assessment of subject eligibility during screening. For this endpoint therefore only investigator reported information is used.

As a result of is interpreted in the SAP as: the HHE assessment is the main reason for subject being non-eligible for enrollment. For all subjects who are ineligible for enrollment investigator fills out maximum three failed Inclusion/Exclusion Criteria in the EDC, the first one filled out is considered to be the *main reason*. Thus, if as first failed IC/EC Criteria Exclusion above cited Inclusion criteria 5 is indicated, the HHE is the main reason for subject.

The endpoint is thus met if these two conditions both apply:

- HHE analysis performed by investigator indicates subject is considered ineligible (refer to SAP section 9.2.5.2) *and*
- The HHE assessment is filled out by investigator in the EDC as being the main reason for subject being ineligible in the trial.

The endpoint is reported for subjects included in the HHE population for whom the HHE assessment resulted in the conclusion ‘Eligible’ or ‘Non Eligible’, meaning subjects are excluded if assessment resulted in “Not Assessable”.

For these subjects the number of and percentage of subjects who were classified as “Ineligible” are reported, as is the number and percentage of subjects who meet the endpoint (being “Ineligible” with the HHE Echo results as main reason for being Ineligible for enrollment).

### **9.2.4.4 *Time from HHE administration to availability of HHE report/results***

These three time points are registered by investigator in the EDC:

- Time of HHE assessment  
(eCRF: dataset HHE, Column ECDAT)

## FLE-002 (INSTANT) – Final Analysis

## Statistical Analysis Plan

-Time HHE report/results are available

*Defined as: Time when results were completed in the source worksheets (eCRF: dataset HHE, column REPDAT)*

-Analysis time

*Defined as the time analysis was completed (eCRF: dataset HHE, Column ANALDAT)*

All three are date-time variables, with number of seconds as measuring unit.

The time from HHE administration to availability of HHE report/results will be reported in minutes and will be calculated as:

$$t_1 = (\text{Time HHE report/results available} - \text{Time of HHE assessment})/60$$

The number of available observations and the mean and standard deviation will be reported.

Additionally the time from HHE administration to time of Analysis will be calculated.

$$t_2 = (\text{Analysis Time} - \text{Time of HHE assessment})/60$$

The number of available observations and the mean and standard deviation will be reported.

### 9.2.4.5 *Agreement between eligibility based on HHE analysis investigator and independent reviewer*

Refer to section 9.2.4.3 for the assessment if subject was eligible according to investigator and according to independent reviewer. For both sources the result of the analysis can be: "Eligible", "Non Eligible" or "Not Assessable".

The statistical report will include a 3\*3 table:

	Eligible according to independent review			Total
Eligible according to investigator	Yes	No	Not Assessable	
Yes	N11	N12	N13	N1.
No	N21	N22	N23	N2.
Not Assessable	N31	N32	N33	N3.
Total	N.1	N.2	N.3	N

The percentage agreement is reported in two ways:

The first percentages show agreement using all analyses, meaning also agreement is reached if both raters indicate eligibility is "Not Assessable"

$$p_1 = 100 * (N11 + N22 + N33) / N.$$

**FLE-002 (INSTANT) – Final Analysis****Statistical Analysis Plan**

The number of patients and the percentage agreement will be reported, if required a 95% two-sided Clopper-Pearson confidence interval will be shown.

The second percentages show agreement excluding analyses where raters indicate eligibility is Not Assessable, thus only including analyses where at least one rater concluded that subject was Eligible or Not Eligible.

$p_2=100*(N11+N22/(N-N33))$ .

The number of patients and the percentage agreement will be reported, if required a 95% two-sided Clopper-Pearson confidence interval will be shown.

Additionally, a listing will show a line per subject, indicating for both investigator as independent reviewer the conclusion on eligibility of the subject.

No other inter-rater comparison of HHE characteristics (e.g. LVEF %, LV hypertrophy, refer to section 9.2.4.1 of SAP) is planned.

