## FLE-002 (INSTANT) – Final Analysis

## Statistical Analysis Plan

HHE images were also reviewed and analyzed by an independent reviewer at a later date.

A HHE was performed for 6 subjects; the last HHE was performed on 11 November 2021.

[figure not shown]
The flowchart of the statistical report for INSTANT will show the number of subjects who signed IC for the HHE sub-study (EU) or for whom an HHE was required at screening (US).

The full statistical analysis of the HHE sub-study is described in this version of the SAP. This analysis requires complete information from the HHE, as performed by the investigator and of the HHE analysis and as performed by the independent reviewer.

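### SAP 9.2.4.5: the second HHE agreement percentage (p2) is bracketed wrongly and exceeds 100% once two subjects are rated eligible by both raters

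*SAP*

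**What the plan says.** SAP section 6.2.4 adds an endpoint that is not in the protocol's HHE list: agreement on eligibility between site staff and the independent reviewer. Section 9.2.4.5 sets out its analysis. Each rater's conclusion is eligible, not eligible or not assessable, and the pairs form a 3×3 table with cells N11 to N33 and total N. N11, N22 and N33 count the subjects on whom the raters agree (both eligible, both not eligible, both not assessable).

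Two percentages follow.

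- The first counts joint not-assessable ratings as agreement: "p_1 = 100 * (N11 + N22 + N33) / N".
- The second drops those subjects, and the text explains the restriction as "thus only including analyses where at least one rater concluded that subject was Eligible or Not Eligible". Its formula is "p_2=100*(N11+N22/(N-N33", closed by two parentheses after N33.

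For each percentage the SAP adds that "if required a 95% two-sided Clopper-Pearson confidence interval will be shown". Section 9.2.4.5 also provides a per-subject listing of both conclusions and plans no other comparison between the raters. On numbers, section 1.3 states: "A HHE was performed for 6 subjects".

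**The concern.** Under the usual order of operations the division in p2 applies to N22 alone. N11, normally the largest cell when most screened subjects are eligible, is never divided by anything. The expression is therefore not a proportion: it adds a count to a fraction. A Clopper-Pearson interval cannot be attached to it, because that interval needs a whole number of agreements out of a whole number of pairs.

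At stake is one of only two agreement figures for an endpoint that the SAP itself introduced. It is the only one of the two that does not credit the raters with agreement when neither could assess the images. SAP section 15 provides separate derivation specifications only if required, so the formula in section 9.2.4.5 may be what the programmer works from.

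**Working it through.** **Inputs**

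- Printed formula: p2 = 100 × (N11 + N22/(N − N33)), SAP 9.2.4.5.
- Intended quantity: agreeing pairs among pairs with at least one eligible or not-eligible conclusion, from the text of the same section. The pairs retained number N − N33, and the agreeing ones among them N11 + N22. Hence p2 = 100 × (N11 + N22)/(N − N33).
- N = 6, the number of HHEs performed (SAP 1.3). Section 9.2.4.2 restricts the eligibility analysis to subjects with an HHE, so 6 is the natural total.
- Cell counts: not given in the documents. Those below are assumptions chosen to show the range.

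The SAP states no numerical value of p2, so there is no figure to reproduce.

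**Size of the error in general**

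Printed minus intended = 100 × N11 × (1 − 1/(N − N33)).

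This is zero only if N11 = 0 or if N − N33 = 1. Otherwise the printed formula overstates agreement.

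**Numbers with N = 6**

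| N11 | N22 | N33 | Printed p2 | Intended p2 |
|---|---|---|---|---|
| 4 | 1 | 1 | 100 × (4 + 1/5) = 420% | 100 × 5/5 = 100% |
| 4 | 1 | 0 | 100 × (4 + 1/6) = 416.7% | 100 × 5/6 = 83.3% |
| 3 | 1 | 1 | 100 × (3 + 1/5) = 320% | 100 × 4/5 = 80% |
| 6 | 0 | 0 | 100 × (6 + 0/6) = 600% | 100 × 6/6 = 100% |
| 1 | 1 | 0 | 100 × (1 + 1/6) = 116.7% | 100 × 2/6 = 33.3% |
| 1 | 0 | 0 | 100 × (1 + 0/6) = 100% | 100 × 1/6 = 16.7% |
| 0 | 4 | 0 | 100 × (0 + 4/6) = 66.7% | 100 × 4/6 = 66.7% |

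The general difference checks against the first row: 100 × 4 × (1 − 1/5) = 320, and 420 − 100 = 320.

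**When the result is impossible**

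All 3×3 tables with N = 6 and N33 < 6 were enumerated, 3,002 in total. The printed formula exceeds 100% in 825 of them, with a maximum of 600%. These are exactly the tables with N11 ≥ 2, or with N11 = 1 and N22 ≥ 1. The 825 is a count of possible tables, not a probability, since they are not equally likely. The intended formula lies between 0% and 100% in every one of the 3,002. In the one remaining table, N33 = 6, both formulas divide by zero.

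**Comparison with p1**

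In p1 the three agreeing cells stand in one bracket and the whole bracket is divided by N. The same layout for p2 requires the bracket to close after N22.

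**The case against.** The strongest reply is that this is a typographical slip with no practical consequence. The wording and p1 leave only one sensible reading, and a competent programmer would code that reading. An exact interval would in any case be built from the two counts. A value such as 420% would be noticed at once, and programming is subject to validation (SAP section 9). The 3×3 table and the listing are reported as well, so with 6 HHEs anyone can recompute the figure by hand. The HHE endpoints are exploratory, the independent review plays no part in eligibility decisions, and nothing in the efficacy or safety analyses uses p2.

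Most of this stands, and it limits the importance of the point. It does not make the formula right. Nor is the error always visible: with N11 = 1 and N22 = 0 the printed formula returns 100% whatever the denominator. That would read as perfect agreement and pass a range check, although the intended value with N = 6 and N33 = 0 is 16.7%.

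Two qualifications are fair. The printed formula does not exceed 100% for every table; it is correct when N11 = 0. A bracket displaced when the PDF text was read cannot be wholly excluded. The parentheses as read do balance, however, so a simple dropped character is unlikely.

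**Conclusion.** The point holds. As printed, p2 is not a percentage agreement, and following it literally gives values up to 600% with 6 subjects. It gives the intended value only when N11 = 0 or when a single pair remains in the denominator. The conclusion rests on ordinary operator precedence and on the SAP's own description of what p2 should measure. The percentages quoted also rest on N = 6 and on assumed cell counts. The consequence is confined to one exploratory statistic, but the SAP specifies it and it should be corrected before the final tables are produced.

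**What to change.** In SAP section 9.2.4.5, replace the second formula by p2 = 100 × (N11 + N22)/(N − N33). State that any Clopper-Pearson interval uses N11 + N22 agreements out of N − N33 pairs, and that p2 is not defined when N = N33. If a p2 program already exists, check that it uses this form.

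The cost is moving one closing parenthesis and adding one sentence. No data, population or other analysis changes, and p1 needs no correction.

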### **9.2.5 Exploratory endpoints for Part C PLS study**

These endpoints will be reported for the PLS population (refer to SAP section 8.8).

#### **9.2.5.1 *Proportion of subjects who achieved therapeutic dosing ( $\geq 200$ ng/mL) with the study drug in the Part C Patient-Led Under Medical Supervision***

Due to the small sample size (n=3), this endpoint will not be analyzed, per subject results will be listed.

#### **9.2.5.2 *Feasibility of patient-led self-administration of study drug***

Below endpoints are defined in the protocol.

##### **1) Percent of subjects who consent to the PLS study**

A first overview shows if patient consented to the PLS study, three possible options:

- “Not applicable”
- “Yes”
- “No”

Only for subjects whose initial treatment was performed in Part B or the MLS Part C of the trial numbers and frequencies will be provided. The sample size is all subjects who received inhaled flecainide in Part B or in the MLS Part C.

For the “non applicable” category the reason is specified:

- Subject not Eligible
- Site does not participate in patient-Led study
- Other (Reason will be provided)

**FLE-002 (INSTANT) – Final Analysis****Statistical Analysis Plan**

For the remaining subjects ("Yes", "No") the number and percentage of subjects who consented to the PLS study is reported. The sample size is the number of remaining subjects ("Yes", "No"). For subjects who did not consent the reason will be provided.

For subjects whose initial treatment was performed in Part A of the trial no information is available in the EDC for this endpoint. Only the number of subjects who consented to the PLS study will be provided.

**2) Percent of subjects who withdraw from the study**

For the subjects who consented to the PLS study the End of Study status will be reported. These categories are specified in the eCRF:

- Completed
- Subject received medication in PLS part of Part C due to recurrent AF
- Subject completed the 8 months follow-up period without treatment of recurrent AF
- Adverse Event
- Death
- Physicians Decision
- Lost to Follow-up
- Withdrawal by Subject
- Protocol Deviation
- Site Terminated by Sponsor
- Study Terminated by Sponsor
- Screen Failure
- Other (the reason will be specified)

Information is available for all subjects participating in the PLS study.

**3) Percent of subjects who are certified for self-administration of study drug**

The number of subjects who consented to the PLS study will be reported as is the number and percentage of subjects who completed training certification.

percentage=100\*number of certified/number of consented subjects

Information is available for all subjects participating in the PLS study.

**4) Percent of subjects who return to clinic with a recurrent episode of PAF within 8 months of signing consent, and the associated timeframe(s) to time(s) of recurrence**

For subjects who consented to the PLS study all AF recurrences after Informed are reported in a listing.

If no AF recurrence occurred subject will be listing as having no AF recurrence.

If any AF recurrence occurred for subject all AF recurrences are shown, one line per recurrence. The line includes:

## FLE-002 (INSTANT) – Final Analysis

## Statistical Analysis Plan

- Subject ID
- Visit when the AF recurrence was registered
- If more than one AF recurrence for the visit: sequence number
- Date and time of AF recurrence
- Did AF recurrence lead to treatment by inhaled flecainide
- If AF recurrence did not lead to treatment by inhaled flecainide: reason why.  
  This is a comment field, e.g. "conversion with pill in the pocket"

Information is available for all subjects participating in the PLS study.

5) Percent of subjects that independently set up and inhaled study drug according to the provided instructions

For subjects receiving inhaled flecainide in the PLS trial investigator filled out:

"Did the subject self-administer the dose as instructed without assistance"

The number and percentage of subjects for whom "Yes" is filled out is reported. For subjects for whom "No" is filled out, a comment field lists the difficulties encountered during self-administration

Information is available for all subjects participating in the PLS study who received inhaled flecainide in the PLS trial.

### **9.2.5.3 *Proportion of subjects whose AF converted to SR***

For subjects receiving inhaled flecainide in the PLS trial the number of subjects who converted to SR within 90 minutes post end of dose is reported, as is the method of Cardioversion (refer to SAP section 3.2)

Information is available for all subjects participating in the PLS study who received inhaled flecainide in the PLS trial.

### **9.2.5.4 *Hand Held Echo (HHE) Endpoints***

- 1) Proportion of subjects for whom capture and assessment of a diagnostic echocardiogram using a HHE at screening was successful
- 2) Percent of subjects who are considered ineligible for enrollment as a result of the HHE assessment
- 3) Time from HHE administration to availability of HHE report/results

In the Part C PLS study no HHE was performed, endpoints will not be reported.

**FLE-002 (INSTANT) – Final Analysis****Statistical Analysis Plan****9.3 On Pooled results (Part A, Part B and Part C MLS Subjects (120 mg FlecIH-103))**

In Part B, a formal homogeneity test was performed to assess if the primary endpoint results for part A subjects receiving the 120 mg FlecIH-103 inhalation solution could be pooled with the primary endpoint results for Part B subjects. If results could be pooled, as was the case, a Total column would be included in the statistical report showing results for the Pooled population of Part A and Part B 120 mg FlecIH-103 subjects.

In the final report MLS subjects from Part A, Part B and Part C MLS will be pooled without any formal test performed on heterogeneity. Refer to sections 8 and 8.7 of SAP for the definition of the pooled cohorts and for an indication per type of data for which pooled cohorts study information will be reported.

**10 Difference between protocol and SAP**

The SAP is in accordance with study protocol V8.0/ EU-1 except for the following deviations:

- The SAP adds Methods for Cardioversion (refer to SAP section 3.2)
- The SAP specifies cohorts of the pre-specified study populations to be analyzed (refer to Table 1 in Section 8.0)
- Only 3 subjects were treated with study medication in the PLS study, as a result for some endpoints results are only listed and no summarizing statistics will be reported
- No HHE data are available for the PLS study, the endpoints will thus not be reported
- The protocol indicates a 90% confidence interval will be created for endpoints, instead (refer to SAP sections 9.2) for a selection of endpoints a 95% confidence intervals will be created; only for the primary efficacy endpoint (refer to SAP section 9.2.1) a 90% confidence interval will be created.
- The protocol indicated  $t_{max}$  is measured as the time to Cmax (from the time of end of dosing), in the SAP definition  $t_{max}$  is measured as the time to Cmax (from the time of the start of dosing).
- Adverse Events of Special Interest (AESI) and Serious Adverse Events of Special Interest (SAESI) will be tabulated using results as indicated in SAP section Annex A, using a slightly different definition than the definition in protocol V8.0/EU-1.

**FLE-002 (INSTANT) – Final Analysis****Statistical Analysis Plan****11 Changes in the Planned Analyses**

Additional analyses that may be included in the Clinical Study Report but are not mentioned in the SAP will be identified as such.

**12 Programming Conventions**

- Identification of analysis population: Every summary table and figure should clearly specify the analysis population being summarized.
- Group headers: In summary tables group headers will identify the summary group and the sample size for the indicated analysis population. The header's sample size does not necessarily equal the number of subjects actually summarized within any given summary module; some subjects in the analysis population may have missing values and thus may not be summarized.
- Presentation of sample sizes: All TFLs should indicate, in one way or another, the number of subjects actually contributing to the summary statistics presented in any given summary module. As mentioned above, this may be less than the number of subjects in the analysis population due to missing data.
  - In the quantitative modules describing continuous variables (and thus presenting sample size, means, and standard deviations), the sample size should be the number of non-missing observations. The number of missing observations, if any, should be identifiable in the module
  - For categorical variables that are presented in frequency tables, the module should present the total count in addition to the count in each category. Percentages should be calculated using this total as the denominator, and the percentage corresponding to the sum itself (that is, 100%) should be presented so as to indicate clearly to a reviewer the method of calculation. The number of missing observations, if any, will be noted.
- Sorting: Listings will be sorted by subject identifier and (where applicable) then by date within each subject identifier. If a listing is sorted in a different manner, a footnote will indicate as such.
- General formatting rules: Rounding for all variables will occur only as the last step, immediately prior to presentation in listings, tables, and figures. No intermediate rounding will be performed on derived variables. The standard rounding practice of rounding numbers ending in 0-4 down and numbers ending in 5-9 up will be employed.
- The presentation of numerical values will adhere to the following guidelines:
  - Raw measurements will be reported to the number of significant digits as captured in the source data
  - Mean, standard deviation, median, Q1 and Q3 will all be shown using 1 additional decimal compared to the source data, with a maximum of two decimals. Minimum and maximum will be shown using the number of decimals in the source data.

## FLE-002 (INSTANT) – Final Analysis

## Statistical Analysis Plan

- Calculated percentages will be reported to one decimal place.
- Dates will be formatted as DDMMYY. Partial dates will be presented on data listings as recorded in the EDC.
- Time will be presented according to the 24-hour clock (HH:MM or HH:MM:SS as applicable).

## 13 References

This version of the SAP only uses references to the study protocol indicated at page 2 of SAP.

## 14 Tables, Figures and Listings

The Tables, Figures and Listings and Flowchart that are included in the final statistical analysis will be created using the analysis described in this SAP. The final report will include an overview of all TFLs that are included in the report.

Each table will reference an associated listing containing data used by the table. If applicable, the figures will reference an associated listing and/or an associated table used by the figure.

For the **MLS** part of the trial all data for subjects that received FlecIH-103 120 mg dose from Parts A, B and C will be included in the listings. If subject also participated in the PLS trial, the results of the PLS trial are not included in the MLS part of the final report.

For the **PLS** part of the trial, the tables and listings will only report on study results for this PLS part of the trial, not for the study results of the initial MLS treatment of subject in Part A, B or Part C MLS. However, for the PLS subjects the MLS study results can be found in these listings:

- If the MLS treatment took place in Part B or Part C MLS: results are listed in the final MLS report under the same subject identifier as in the PLS report
- If MLS treatment took place in Part A and in Part A subject received 2\*60 mg FlecIH-103 (and is thus included in the pooled MLS analysis): results are listed in the final MLS report. Subject however received a new subject identifier in Part C PLS, the PLS report will include information showing the subject identifier in the PLS report and the corresponding subject identifier in the final MLS report
- If MLS treatment took place in Part A and in Part A subject received a different regimen than 2\*60 mg FlecIH-103 (and is thus not included in the pooled MLS analysis): results were listed in the final report for Part A of the trial (as created July 24, 2020). Subject however received a new subject identifier in Part C PLS, the PLS report will include information showing the subject identifier in the Part C PLS report and the corresponding identifier in the final Part A report.

---

